12.5.2 Safety endpoints

For all safety analyses, the SAF will be used. All listings and tables will be presented by treatment group.

Safety summaries (tables, figures) include only data from the on-treatment period with the exception of baseline data which will also be summarized where appropriate (e.g., change from baseline summaries). In addition, a separate summary for death including on treatment and post treatment deaths will be provided. In particular, summary tables for adverse events (AEs) will summarize only on-treatment events, with a start date during the on-treatment period (treatment-emergent AEs).

The on-treatment period lasts from the date of first administration of study treatment to 28 days after the date of the last actual administration.

Due to the open-label period after the double-blind period, the on-treatment double-blind period will stop at the earliest on:

- the date of the last actual dose intake of remibrutinib double-blind
- the date of first dose intake of open-label treatment

Adverse events

All information obtained on adverse events will be displayed by treatment group and participant.

The number (and percentage) of participants with treatment emergent adverse events (events started after the first dose of study medication or events present prior to start of double-blind treatment but increased in severity based on preferred term) will be summarized in the following ways:

- by treatment, primary system organ class and preferred term.
- by treatment, primary system organ class, preferred term and maximum severity.
- by treatment, Standardized MedDRA Query (SMQ) and preferred term.

Separate summaries will be provided for study medication related adverse events, death, serious adverse events, other significant adverse events leading to discontinuation by treatment group and study period.

The number (and proportion) of participants with adverse events of special interest for remibrutinib (related to identified and potential risks) will be summarized by treatment group and study period.

A participant with multiple adverse events within a primary system organ class is only counted once towards the total of the primary system organ class.

Vital signs

All vital signs data will be listed by treatment group, participant, and visit/time and if ranges are available, abnormalities (and relevant changes) will be flagged. Summary statistics will be provided by treatment and visit.

[figure not shown]
12-lead ECG

PR, QRS, QT, QTcF, and RR intervals will be obtained from 12-lead ECGs for each participant during the study. ECG data will be read and interpreted centrally.

All ECG data will be listed by treatment group, participant and visit/time, abnormalities will be flagged. Summary statistics will be provided by treatment and visit/time.

Clinical laboratory evaluations

All laboratory data will be listed by treatment group, participant, and visit and if normal ranges are available abnormalities will be flagged. Summary statistics for the change from baseline will be provided by treatment and visit. Shift tables using the low/normal/high/ (low and high) classification will be used to compare baseline to the worst on-treatment value.

[REDACTED]

[REDACTED]

[REDACTED]

[REDACTED]

[REDACTED]

12.5.7 Patient reported outcomes

[REDACTED]

[REDACTED]

[REDACTED]

Dermatology Life Quality Index (DLQI)

[REDACTED]

The proportion of participants achieving DLQI = 0-1 will be provided by treatment group and visit.

[REDACTED]

12.7 Interim analyses

A primary analysis may be conducted when all participants have completed their Week 24 visit or discontinued early and when a minimum of 150 participants across both Phase 3 pivotal studies have completed the treatment period (a second, nearly identical Phase 3 study will be conducted in parallel). The minimum of 150 participants reaching week 52 should enable analysis on a minimum of 100 participants exposed to remibrutinib for 52 weeks, considering the initial randomization to either the remibrutinib or the placebo arm (2:1). The results of the primary analysis will further inform decision-making for the remibrutinib development program. Formal testing of the primary endpoint and key secondary endpoints will only be performed at the primary analysis time point; thus, no adjustment for multiplicity is required.

After the primary analysis and/or after all participants entered the open label treatment period, additional optional interim analyses may be conducted at the discretion of the Sponsor to support potential Health Authority requests and interactions (these interim analyses are not expected to have any impact on the conduct or scientific integrity of the study). The decision to conduct optional interim analyses and the timing of these analyses will be documented in the Statistical Analysis Plan prior to the conduct of any interim analysis. These interim analyses will be performed and interpreted by members of the Novartis clinical team.

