This is a global, multicenter, randomized, double-blind, parallel-group, placebo-controlled Phase 3 study investigating the safety, tolerability, and efficacy of remibrutinib (25 mg b.i.d.) in adult participants with CSU inadequately controlled by second generation H1-antihistamines. The study consists of four periods, the total study duration is up to 60 weeks (Figure 3-1):

- **Screening period:** up to 4 weeks.
- **Double-blind treatment period:** 24 weeks of double-blind treatment with remibrutinib (25 mg b.i.d.) or placebo.
- **Open-label treatment period:** 28 weeks of open-label treatment with remibrutinib (25 mg b.i.d.).
- **Follow-up period:** 4 weeks of treatment-free follow-up.

The primary analysis may be conducted after all participants have completed Week 24 or discontinued earlier and when a minimum of 150 participants across both Phase 3 pivotal studies (a second, nearly identical Phase 3 study will be conducted in parallel) have completed the treatment period at Week 52 (see Section 4.4). **All participants will be on a stable, locally label approved dose of a second generation H1-antihistamine (“background therapy”) throughout the entire study (starting a minimum of 7 days prior to randomization until the end of the study).** To treat unbearable symptoms of CSU, participants will be allowed to use another second generation H1-antihistamine on an as-needed basis (“rescue therapy”). Eligible participants will be randomly assigned to the treatment arms in a 2:1 ratio. The study population will consist of approximately 450 female and male adult participants (300 in the active arm and 150 in the placebo arm) with CSU inadequately controlled by second generation H1-antihistamines at least at locally label approved dose. Participants will be stratified based on prior exposure to anti-IgE biologics and geographic region.

An extension study is in development. Eligible participants may roll over at Week 52 (after completing 52 weeks of treatment and all scheduled assessments planned at this visit). The details of the study design and procedures of the extension, if implemented, will be described in a separate protocol.

Figure 3-1 Study Design

D-1: Day 1, b.i.d.: bis in die/twice a day, mg: milligram(s), Pbo: placebo, PA: Primary Analysis, PE: Primary Endpoint, Scr: Screening, W: Week

4 Rationale

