4.6 Rationale for Public Health Emergency mitigation procedures

During a Public Health emergency as declared by Local or Regional authorities, i.e., pandemic, epidemic or natural disaster, mitigation procedures to ensure participant safety and trial integrity are listed in relevant sections. Notification of the Public health emergency should be discussed with Novartis prior to implementation of mitigation procedures, and permitted/approved by Local or Regional Health Authorities and Ethics Committees as appropriate.

5 Study Population

The study population will consist of approximately 450 randomized female and male adult participants (300 in the active arm and 150 in the placebo arm) with CSU inadequately controlled by second generation H1-antihistamines (at least at locally label approved dose).

The screen failure rate is estimated to be 30%, meaning approximately 645 participants are expected to be screened.

Participants will be stratified based on prior exposure to anti-IgE biologics and geographic region; maximum number of participants with prior exposure to anti-IgE biologics will be limited to approximately 30% of the total study population.

Participants who drop out after they have been randomized will not be replaced.

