6.1.3 Treatment arms/group

Participants will be assigned at Day 1 to either remibrutinib 25 mg b.i.d. or matching placebo in a ratio of 2:1. At week 24 participants in the placebo arm will be switched to active treatment. Each participant will take one film-coated tablet in the morning and one film-coated tablet in the evening [REDACTED]

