12.8 Sample size calculation

12.8.1 Primary endpoint(s)

In order to fulfill registration and ICH E1 requirements on the number of participants treated for 6 months and 12 months in the development program, a sample size of 300 participants in the active arm and 150 in the placebo arm is targeted. Hence, the total sample size is 450 randomized participants.

From an efficacy point of view, the sample size justification is based on UAS7 change from baseline (for scenario with one primary endpoint), ISS7 and HSS7 change from baseline (for scenario with co-primary endpoints) and achievement of $UAS7 \leq 6$ and $UAS7 = 0$ at Week 12. To avoid assigning an unnecessary large number of participants to placebo, participants will be randomized in a 2:1 ratio to remibrutinib 25 mg b.i.d. and placebo arms, respectively.

[REDACTED]

All calculations were performed with nQuery Advisor 8.4.1.0 and Ri386 4.0.2 softwares.

For scenario with UAS7 as the primary efficacy endpoint

UAS7 change from baseline at Week 12

Approximately 10% drop-out is expected at week 12, thus with 270 participants in the active arm and 135 participants in the placebo arm, this gives a nominal power of more than > 99% to detect a difference between remibrutinib and placebo if the mean change of UAS7 from baseline to Week 12 is at least 10 in favor of remibrutinib, with common standard deviation of approximately 12 (based on the primary endpoint analysis of Phase 2b study (CLOU064A2201)), based on a t-test, assuming type I error 0.025 (one-sided).

For scenario with ISS7/HSS7 as the co-primary efficacy endpoints

ISS7 change from baseline at Week 12

Approximately 10% drop-out is expected at week 12, thus with 270 participants in the active arm and 135 participants in the placebo arm, this gives a nominal power of more than > 99% to detect a difference between remibrutinib and placebo if the mean change of ISS7 from baseline to Week 12 is at least 4 in favor of remibrutinib, with common standard deviation of approximately 6 (based on the primary endpoint analysis of Phase 2b study (CLOU064A2201)), based on a t-test, assuming type I error 0.025 (one-sided).

HSS7 change from baseline at Week 12

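### At 150 Week-52 completers, 100 on remibrutinib for 52 weeks is the expected number under 2:1 allocation, not the minimum the plan states

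*Protocol*

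**What the plan says.** Protocol 12.7 sets two conditions for the primary analysis. The first is "A primary analysis may be conducted when all participants have completed their Week 24 visit or discontinued early". The second is that "a minimum of 150 participants across both Phase 3 pivotal studies have completed the treatment period". The purpose of the second is then stated: "The minimum of 150 participants reaching week 52 should enable analysis on a minimum of 100 participants exposed to remibrutinib for 52 weeks". The one reason offered is the 2:1 initial randomisation. Protocol 4.4 and SAP 2.13 carry the same sentence. None of the three places gives a margin, an assurance level or a direct count of remibrutinib-arm completers.

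Two other places bear on the point. Protocol 6.1.3 says "At week 24 participants in the placebo arm will be switched to active treatment", and Protocol section 3 gives the open-label period as 28 weeks. Protocol 12.8.1 opens its sample-size rationale with "In order to fulfill registration and ICH E1 requirements on the number of participants treated for 6 months and 12 months", and refers there to the development program as a whole.

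**The concern.** A threshold chosen so that a minimum is met should meet it with high probability. This one is set where the minimum equals the mean, so at the threshold a shortfall is nearly as likely as not. A blinded team that sees 150 completers could believe that 100 participants with 52 weeks on remibrutinib were assured when they were not. What is at stake is the size of the 52-week exposure group available at the primary analysis, which is the stated reason for having the threshold.

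**Working it through.** **Inputs from the documents.** Trigger: 150 completers pooled over both studies (Protocol 12.7). Allocation: 2:1, so the remibrutinib share is 2/3. Arm sizes in this study: 300 and 150 (Protocol section 5). Drop-out: about 10% by Week 12, applied to both arms (Protocol 12.8.1); no Week-52 figure is given. Randomisation is stratified by prior anti-IgE use and region, with no block size stated (Protocol 6.4.2).

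**Assumptions.** Retention to Week 52 is equal in the two arms. The second study, described as nearly identical, also randomises 450 participants 2:1.

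**1. The plan's figure.** 150 × 2/3 = 100.0. It reproduces exactly, as an expected value.

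**2. Placebo-arm completers.** 52 − 24 = 28 weeks on remibrutinib at Week 52. They do not count towards 52-week exposure.

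**3. Spread at exactly 150.** With X ~ Binomial(150, 2/3), SD = √(150 × 2/3 × 1/3) = 5.8. The central 95% range is 89 to 111, and P(X ≥ 100) = 0.538. Drawing 150 without replacement from 900 participants, 600 of them on remibrutinib (hypergeometric), gives 0.541.

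**4. More than 150 completers at the cut.**

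| Completers | Expected on remibrutinib | P(≥ 100), binomial | P(≥ 100), hypergeometric |
|---|---|---|---|
| 150 | 100.0 | 0.54 | 0.54 |
| 155 | 103.3 | 0.74 | 0.76 |
| 160 | 106.7 | 0.88 | 0.91 |
| 165 | 110.0 | 0.96 | 0.97 |
| 180 | 120.0 | > 0.999 | > 0.999 |

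The smallest binomial trigger is 157 for 80% assurance, 161 for 90% and 165 for 95%.

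**5. Blocked allocation.** Permuted blocks reduce the spread. Simulations with blocks of 3 or 6, 20 strata and 52-week retention of 75% to 100% (all assumed) gave an SD of 1.7 to 3.3 and P(≥ 100) of 0.55 to 0.61 at 150. The lower 2.5% point was 94 to 97, a shortfall of 3 to 6, against 11 under the binomial. Using a normal approximation, 95% assurance needs 2n/3 − 1.645 × SD ≥ 99.5. That gives n = 154 for SD 1.7 and n = 158 for SD 3.3.

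**6. Unequal retention (assumed).** The remibrutinib share of completers is 2(1 − a) / [2(1 − a) + (1 − b)], where a and b are the 52-week drop-out rates on remibrutinib and placebo. P(≥ 100) at 150 is then:

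- a = 10%, b = 15%: share 0.679, probability 0.67
- a = 10%, b = 20%: share 0.692, probability 0.78
- a = 15%, b = 10%: share 0.654, probability 0.41
- a = 20%, b = 10%: share 0.640, probability 0.28

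The documents do not say which direction to expect.

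**7. Whether the cut would fall at 150.** The Amendment 1 rationale (23 May 2022) reports 123 participants randomised in this study. They would reach Week 52 by about late May 2023. SAP amendment 4, dated 30 June 2023, is logged as before the primary analysis. So up to 123 completers could have come from this study by then, leaving 150 − 123 = 27 to come from the second study if all were retained. Retention, the data cut-off date and the second study's accrual are not given.

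**The case against.** The strongest reply is that the 54% describes one stopping point that may never occur. The figure of 150 is itself a floor, all participants must also be past Week 24 or have discontinued, and the analysis is permitted rather than required once both conditions hold. The dates in step 7 suggest that the count could well pass 150 before the Week-24 condition is met. This stands as a limit on the consequence. It is not proof, since the cut-off date and the other study's accrual are missing, and the plan does not use this argument to support its figure.

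The wording that 150 should enable a minimum of 100 can also be read as an expectation rather than a guarantee. That is fair, but an expectation of a minimum is still not an expected value.

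A reader might infer that a primary analysis cut at 150 would fail the ICH E1 exposure requirement almost half the time. The documents do not support that. Protocol 12.8.1 ties ICH E1 to the whole development program and uses it to justify the 300-participant active arm. It neither names 100 nor says that the number must be met at this analysis. More participants reach Week 52 before the final analysis.

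A reader might also expect lower retention on remibrutinib to make matters worse. The documents give no basis for that direction, and the opposite direction raises the probability (step 6). The binomial triggers ignore blocking, so they may be higher than needed (step 5).

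**Conclusion.** The point holds in a limited form. On the plan's own inputs, 100 is the mean number of remibrutinib-arm completers among 150 and is reached about 54% of the time at exactly 150 with equal retention. Assumed blocking moves this only to 0.55 to 0.61. The stated minimum is therefore not supported by its stated reason.

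The size is small. At the lower 2.5% point the shortfall is about 11 participants under independent allocation and about 3 to 6 under the assumed blocking. The probability rises quickly with each few completers beyond 150. The point affects only the long-term exposure count at the primary analysis. The Week 12 estimands, power, testing hierarchy and type I error are untouched, so it gives no reason to doubt the efficacy result.

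**What to change.** Change Protocol 4.4, Protocol 12.7 and SAP 2.13 together, in one of two ways:

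- **Preferred.** Define the trigger as at least 100 participants randomised to remibrutinib, across both studies, having completed Week 52. The independent analysis team that Protocol 6.5 already gives randomisation access for the DMC reports could confirm the count, so the study team stays blinded.
- **If the trigger must stay blinded.** Raise 150 to about 160 to 165, and state the assurance and the allocation model behind it. If the actual block sizes support it, a lower figure may do; the assumed blocks in step 5 point to about 154 to 158.

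At minimum, replace the stated minimum with *approximately 100 expected* and report the actual number with 52 weeks on remibrutinib at the cut-off. SAP amendment 5 (24 January 2024) is logged as before the final analysis, which suggests that the primary analysis may already have taken place. If so, only this minimum change remains useful.

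The cost is wording in three places and possibly a short delay to the primary analysis. No extra participants are needed.

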12.8 Sample size calculation

12.8.1 Primary endpoint(s)

In order to fulfill registration and ICH E1 requirements on the number of participants treated for 6 months and 12 months in the development program, a sample size of 300 participants in the active arm and 150 in the placebo arm is targeted. Hence, the total sample size is 450 randomized participants.

From an efficacy point of view, the sample size justification is based on UAS7 change from baseline (for scenario with one primary endpoint), ISS7 and HSS7 change from baseline (for scenario with co-primary endpoints) and achievement of $UAS7 \leq 6$ and $UAS7 = 0$ at Week 12. To avoid assigning an unnecessary large number of participants to placebo, participants will be randomized in a 2:1 ratio to remibrutinib 25 mg b.i.d. and placebo arms, respectively.

[REDACTED]

All calculations were performed with nQuery Advisor 8.4.1.0 and Ri386 4.0.2 softwares.

For scenario with UAS7 as the primary efficacy endpoint

UAS7 change from baseline at Week 12

Approximately 10% drop-out is expected at week 12, thus with 270 participants in the active arm and 135 participants in the placebo arm, this gives a nominal power of more than > 99% to detect a difference between remibrutinib and placebo if the mean change of UAS7 from baseline to Week 12 is at least 10 in favor of remibrutinib, with common standard deviation of approximately 12 (based on the primary endpoint analysis of Phase 2b study (CLOU064A2201)), based on a t-test, assuming type I error 0.025 (one-sided).

For scenario with ISS7/HSS7 as the co-primary efficacy endpoints

ISS7 change from baseline at Week 12

Approximately 10% drop-out is expected at week 12, thus with 270 participants in the active arm and 135 participants in the placebo arm, this gives a nominal power of more than > 99% to detect a difference between remibrutinib and placebo if the mean change of ISS7 from baseline to Week 12 is at least 4 in favor of remibrutinib, with common standard deviation of approximately 6 (based on the primary endpoint analysis of Phase 2b study (CLOU064A2201)), based on a t-test, assuming type I error 0.025 (one-sided).

HSS7 change from baseline at Week 12

Approximately 10% drop-out is expected at week 12, thus with 270 participants in the active arm and 135 participants in the placebo arm, this gives a nominal power of more than > 99% to detect a difference between remibrutinib and placebo if the mean change of HSS7 from baseline to Week 12 is at least 4 in favor of remibrutinib, with common standard deviation of approximately 6 (based on the primary endpoint analysis of Phase 2b study (CLOU064A2201)), based on a t-test, assuming type I error 0.025 (one-sided).

With 300 participants in the active arm and 150 participants in the placebo arm randomized in this study, this gives a power of more than > 90% to detect a difference between remibrutinib and placebo in both mean change of ISS7 and HSS7 from baseline to Week 12 when correlation between endpoints is 0 (conservative assumption, as higher the correlation is, higher the power is).

12.8.2 Secondary endpoint(s)

Achievement of UAS7 = 0 at Week 12

Similarly, with approximately 10% drop-out at week 12, then with 270 participants in the active arm and 135 participants in the placebo arm, this gives a nominal power of more than > 99% to detect a difference between remibrutinib and placebo arm assuming a proportion of complete response (UAS7 = 0) of 0.35 in the remibrutinib arm and of 0.10 in the placebo arm, based upon a 2-group continuity corrected χ^2 test with a 0.025 one-sided significance level.

Achievement of UAS7 \leq 6 at Week 12

Similarly, with approximately 10% drop-out at week 12, then with 270 participants in the active arm and 135 participants in the placebo arm, this gives a nominal power of more than > 99% to

detect a difference between remibrutinib and placebo arm assuming a proportion of disease activity control response ($UAS7 \leq 6$) of 0.53 in the remibrutinib arm and of 0.15 in the placebo arm, based upon a 2-group continuity corrected χ^2 test with a 0.025 one-sided significance level.

The primary and secondary endpoints analyses are planned to use the multiple testing strategy to control the family-wise error at $\alpha = 0.025$ (one-sided). It is considered, however, this hierarchical approach could impact the sample size compared to the separate endpoint approach, which depends on how the recycled alpha will be used. In both scenarios, the “family-wise” power (power to reject all null hypotheses) is $> 90\%$ when correlation between endpoints is 0 (Higher the correlation is, higher the power is).

13 Ethical considerations and administrative procedures

